6.6 Missing Data

All possible efforts will be made to minimize missing data in this study. However, based on previous studies, any missing data that does occur is likely due to missed follow-up visits. Since each subject receives both treatments, differential follow-up by treatment is unlikely to be systematic. However, the sensitivity of the final results to missing data will be examined by comparing the primary outcomes to the results using a longitudinal model with both the 30-day and 60-day post treatment results, and a tipping-point analysis will be performed for the endpoints at 60 days to determine whether the missing data could change the inference compared to the primary models.

6.7 Exploratory Analysis

6.7.1 Lesion Clearance

The Lesion Clearance Scale will be used by blinded site investigators to classify the degree of lesion clearance at 30 and 60 days post last treatment. A 4-point scale (0,1,2,3) will be used to characterize each lesion as “Clear”, “Mostly Clear”, “Partially Clear”, or “Not Clear”.

Lesion Clearance Scale			
CLEAR	MOSTLY CLEAR	PARTIALLY CLEAR	NOT CLEAR
0	1	2	3

The number and proportion at each level of response will be tabulated, and the proportion of lesions with clearance response will be compared across treatment groups using a model similar to the primary effectiveness outcome (**Section 6.1.2**). Clearance response is defined as scores of 0 or 1 (“Clear” or “Mostly Clear”) versus non-response defined as scores of 2 or 3 (“Partially Clear” or “Not Clear”). This endpoint is collected for comparison to previous trials, which used the Lesion Clearance Scale.

6.7.2 Subject-Level Safety Events at 30 Days Post-Last Treatment

Subjects will be classified based on the presence or absence of hyperpigmentation, hypopigmentation or scarring at 30 days after the last treatment. Subjects will be counted once per treatment (that is, per randomized side of face) based on whether any lesion treated with electrodesiccation or CellFX experiences hyperpigmentation, hypopigmentation or scarring at 30 days after the last treatment. The number and percentage of subjects in each of the following categories will be tabulated:

- Subjects with no events for either treatment
- Subjects with an event in at least 1 CellFX-treated lesion but no events in any electrodesiccation-treated lesion
- Subjects with an event in at least 1 electrodesiccation-treated lesion but no events in any CellFX-treated lesion
- Subjects with events in both electrodesiccation and CellFX-treated lesions

This tabulation will be performed using the ITT population, but lesions will be classified as treated with CellFX or electrodesiccation based on the actual treatment received for each lesion.

6.7.3 Subject-Level GAIS Response at 30 Days Post-Last Treatment

Subjects will be classified based on whether all treated lesions respond to treatment (defined as a score of ‘4’ or ‘5’ on the GAIS scale) at 30 days after the last treatment. Subjects will be counted once per treatment (that is, per randomized side of face) based on whether all lesions treated with electrodesiccation or CellFX respond to treatment at 30 days after the last treatment. The number and percentage of subjects in each of the following categories will be tabulated:

- Subjects with at least 1 lesion failing to respond in each treatment
- Subjects with GAIS response for all CellFX-treated lesions but failure to respond for any electrodesiccation-treated lesion
- Subjects with GAIS response for all electrodesiccation-treated lesions but failure to respond for any CellFX-treated lesion
- Subjects with GAIS response for all lesions treated with electrodesiccation and CellFX-treated lesions

This tabulation will be performed using the ITT population, but lesions will be classified as treated with CellFX or electrodesiccation based on the actual treatment received for each lesion.

7.0 CLINICAL PHOTOGRAPHY

The Sponsor will use Canfield Scientific, Inc. to provide photography equipment and services to the study sites. Three close-up photographs (left, right and frontal) at each study visit will be taken with the VISIA-CR system. In order to ensure consistent serial clinical photography is achieved during the study, all subject photographs will be reviewed (monitored) on an ongoing basis. Digital images will be transferred to Canfield via the secure website.

8.0 INDEPENDENT PANEL REVIEW

To meet the requirements of the secondary endpoint, an Independent Panel will evaluate the treatment response from each study device. In order to enhance objectivity and reduce potential for bias, the Panel shall be independent of the Sponsor as well as the study sites/investigators.

The Panel is made up of three clinicians with pertinent expertise in dermatology who are not participants in the study and who do not have any other real or potential conflicts of interest. The Panel will be provided photographs of all study lesions at baseline and 60 days post last treatment and will be trained on specific criteria used to classify the response to treatment as noted in **Section 6.2**.

An Independent Panel review will be conducted by Canfield Scientific based on prior standard methodology.

9.0 ADVERSE EVENTS

Pulse Biosciences will classify each reported Adverse Event according to ISO 14155:2011. All protocol specific AEs, whether device-related or not, will be recorded on the AE case report form and reported. Data to be collected will include the description of the AE, onset, and resolution dates (or whether the AE is ongoing), severity, management/treatment, outcome, and determination of the relationship to the device and/or procedure. All AEs related to the lesion site(s) should be reported and classified by the blinded site Investigator and to be followed by the treating Investigator to determine the relationship of the AE to the device or the study procedure.

All AE information will be collected from enrollment through 60 days following the last CellFX and Electrodesiccation procedures. All AEs will be followed until the event has resolved (in the case of permanent impairment, the event will be followed until it stabilizes, and the overall clinical outcome has been ascertained).

When reporting AEs/SAEs, the Investigator should include the following information:

- Description of event
- Onset of event
- Duration of event
- Severity
- Relationship to device or procedure
- Action taken
- Subject outcome

Severity describes the intensity of an event and will be assessed as:

- **Mild:** The AE does not interfere in a significant manner with the subject's normal functioning level.
- **Moderate:** The AE produces some impairment of function but not hazardous to health.
- **Severe:** The AE produces significant impairment of function or incapacities and/or it is a hazard to the subject.

Relationship to device or procedure will be assessed as:

- **Unlikely:** There is no indication that the AE was caused by the investigational or standard of care device.
- **Possibly:** It cannot be excluded that the AE was caused by the investigational or standard of care device.
- **Likely:** A causal relationship between the investigational or standard of care device and the AE is at least a reasonable possibility; i.e. there is evidence or argument suggesting a causal relationship.

9.1 Adverse Event Definitions

9.1.1 Adverse Event (AE): (ISO 14155:2011 3.2)

Any untoward medical occurrence, unintended disease or injury, or untoward clinical signs (including abnormal laboratory findings) in subjects, users, or other persons, whether or not related to the investigational medical device.

NOTE 1: This definition includes events related to the investigational medical device or the comparator.

NOTE 2: This definition includes events related to the procedures involved.

***For the purposes of this protocol, only dermatologic AEs will be reported to the Sponsor.**

9.1.2 Adverse Device Effect (ADE): (ISO 14155:2011 3.1)

Adverse event related to the use of an investigational medical device

NOTE 1: This definition includes adverse events resulting from insufficient or inadequate instructions for use, deployment, implantation, installation, or operation, or any malfunction of the investigational medical device.

NOTE 2: This definition includes any event resulting from use error or from intentional misuse of the investigational medical device

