3.0 PROTOCOL

3.1 Study Objectives

The primary objective of this study is to compare the safety and effectiveness of the CellFX System to Electrodesiccation (Hyfrecator electrosurgical unit) performed with a non-insulated needle-shaped electrode for removal and treatment of SH lesions in healthy adult subjects.

The following objectives are to evaluate the overall response to CellFX and Electrodesiccation:

- SH lesion response after treatment vs. the pre-treated appearance of the same lesion
- SH lesion response at various points in time over several weeks following the initial treatments vs. the same pre-treated lesion
- Document the condition of skin in the treatment areas (erythema, swelling, crusting, hyperpigmentation, hypopigmentation, etc.) over the course of various time periods post-initial CellFX and Electrodesiccation treatment, and
- Document all safety related issues that may be considered as adverse side effects or serious adverse events

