9.1.3 Serious Adverse Event (SAE) (ISO 14155:2011 3.37)

Adverse event that

- a) led to death,
- b) led to serious deterioration in the health of the subject, that either resulted in
 - 1) a life-threatening illness or injury, or
 - 2) a permanent impairment of a body structure or a body function, or
 - 3) in-patient or prolonged hospitalization, or
 - 4) medical or surgical intervention to prevent life-threatening illness or injury or permanent impairment to a body structure or a body function,
- c) led to fetal distress, fetal death or a congenital abnormality or birth defect.

NOTE 1: Planned hospitalization for a pre-existing condition, or a procedure required by the CIP, without serious deterioration in health, is not considered a serious adverse event.

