9.3 Safety Reporting Requirements

Table 3 summarizes the time sensitive requirements for adverse events and device deficiencies. The Sponsor is the contact person for these reporting requirements.

Table 3. Investigator Responsibilities for Submitting Adverse Events to the Sponsor

Type of Adverse Event	Reporting Timeframe
*Serious Adverse Device Effects (SADE), including Unanticipated Serious Adverse Device Effect (USADE)	As soon as possible, but in no case later than 3 calendar days after the clinical site first learns of the event or of new information in relation with an already reported event
**Serious Adverse Events (SAE)	As soon as possible, but in no case later than 3 calendar days after the clinical site first learns of the event or of new information in relation with an already reported event
Adverse Device Effects (ADE)	As soon as possible, but in no case later than 3 calendar days after the clinical site study team first learns of the event or of new information in relation with an already reported event
All other AEs (dermatologic only)	Submit in a timely manner after the clinical site first learns of the event
**Device Deficiency with SADE potential	As soon as possible, but in no case later than 3 calendar days after the clinical site study team first learns of the deficiency or of new information in relation with an already reported deficiency
All other Device Deficiencies	Submit in a timely manner after the clinical site first learns of the deficiency

*The Sponsor will report the results of an evaluation of an unanticipated serious or serious adverse device effect to the FDA and all reviewing IRBs and investigators within 10 working days after the Sponsor first received notice of the adverse effect per 21 CFR 812.150.

**It is the responsibility of the investigator to inform their IRB of serious adverse events and device deficiencies as required by their IRB guidelines.

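### Section 9.1.1 limits sponsor reporting to dermatologic AEs without exception, while Table 3 in Section 9.3 requires every SAE, SADE/USADE and ADE within 3 calendar days

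*Combined protocol and SAP*

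**What the plan says.** Section 9.1.1 adopts a broad definition of an adverse event: "Any untoward medical occurrence, unintended disease or injury, or untoward clinical signs", related to the device or not. A starred sentence at the end of that subsection, just ahead of the 9.1.2 heading, then narrows what sites send on. For this protocol, "only dermatologic AEs will be reported to the Sponsor". The sentence makes no exception for seriousness or for relation to the device, and it does not mention Table 3.

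Table 3 in Section 9.3 lists what the investigator must submit to the sponsor and when. SADEs (including USADEs), SAEs and ADEs each have an outer limit of 3 calendar days, and none of these rows is limited to skin. The dermatologic restriction appears once in the table, in the row for the remaining events: "All other AEs (dermatologic only)".

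Three other places bear on the point:

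- Section 9.0 says that *protocol specific* AEs are recorded and reported, but the term is not defined.
- Section 11.2 obliges the investigator to follow the reporting requirements of Section 9.3.
- Section 10.5.2 has monitors review events that meet the criteria for serious adverse event reporting.

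**The concern.** The two sections give different answers for the same event. Take an event outside the skin that is serious or is attributed to the CellFX System. Under the wording of 9.1.1 the site does not send it to the sponsor. Under Table 3 the site sends it within 3 calendar days.

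What is at stake is the flow of safety information. The Table 3 footnote starts the sponsor's 10-working-day period for reporting to FDA, IRBs and investigators when the sponsor first receives notice. An event that a site holds back under 9.1.1 would not start that clock. Such events cannot be ruled out from the protocol's own content: the device delivers electrical pulses to the face, and a local anesthetic is used with both treatments (Sections 3.4 and 3.5).

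**Working it through.** No arithmetic applies. The check is whether the restriction in 9.1.1 reaches the categories that Table 3 makes reportable.

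1. **Scope of AE.** Section 9.1.1 covers any untoward medical occurrence, so an AE is not limited to the skin.
2. **ADE.** Section 9.1.2 defines it as "Adverse event related to the use of an investigational medical device". It is a subset of AE, with no skin limit.
3. **SAE.** Section 9.1.3 defines it as an adverse event that led to death, that "led to serious deterioration in the health of the subject, that either resulted in" one of four listed outcomes, or that led to a listed fetal or congenital outcome. It is also a subset of AE, with no skin limit.
4. **SADE.** Section 9.1.4 defines it as an ADE with the consequences of an SAE, so it is a subset of ADE and hence of AE. Table 3 includes USADEs under SADEs.
5. **Consequence.** A rule about which AEs go to the sponsor, stated without exception, applies by its terms to all of these subsets.

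For a non-dermatologic event, the two rules compare as follows:

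| Class of event | Section 9.1.1, read literally | Table 3, Section 9.3 |
|---|---|---|
| SADE, including USADE | not reported to sponsor | within 3 calendar days |
| SAE | not reported to sponsor | within 3 calendar days |
| ADE | not reported to sponsor | within 3 calendar days |
| All other AEs | not reported to sponsor | not reported to sponsor |

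The rules agree on the last row and disagree on the first three. The two device-deficiency rows of Table 3 are left out because the 9.1.1 sentence concerns AEs only.

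6. **Is there a precedence rule?** Section 11.2 directs the investigator to Section 9.3, which favors Table 3. It does not say that 9.3 overrides 9.1.1, and neither does any other section. The phrase *protocol specific* AEs in Section 9.0 does not settle it, because a site could read it as either the broad or the narrow set.
7. **Does it reach the analysis?** The two primary safety endpoints (Section 6.1.1) are lesion-level skin findings recorded by the blinded site investigator. The primary effectiveness endpoint (Section 6.1.2) is GAIS response from photographs. The sample size (Section 6.3) rests on those three endpoints. None of them uses AE reports.

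**The case against.** The strongest reply is that the protocol already shows what was meant. Section 9.3 is the operative reporting section, and Table 3 is written for investigators. It carries the same dermatologic restriction but places it on the residual row alone. The 9.1.1 sentence is a starred remark under the general AE definition, and the subsections on ADE, SAE, SADE and UADE carry no such remark. If the remark is read as covering only the residual class, every rule can be followed. Section 11.2 makes compliance with 9.3 mandatory, Section 10.5.2 has monitors look for serious events, and a Table 3 footnote has the investigator inform the IRB of serious events as its guidelines require. Muscle twitching is asked about after each CellFX-treated lesion, so its capture does not depend on AE reporting.

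Most of this stands. It makes the residual-class reading the likely intent and lowers the chance that an event is lost. It does not remove the conflict, because the reader has to supply the limitation that 9.1.1 omits. Monitoring is also only a partial backstop. Visits are periodic and cannot secure a 3-day deadline, and the event review in 10.5.2 is framed around serious events, so a non-serious, non-skin ADE is less well covered. Section 11.2 does add verification of AEs against source documents, but that too is a monitoring activity.

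A reader might also infer a third conflicting rule from Section 3.1, where an objective is to "Document all safety related issues that may be considered as adverse side effects or serious adverse events". The text does not support that. It concerns what is documented, not what is sent to the sponsor or when, and documenting an event is compatible with limiting which events are forwarded.

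**Conclusion.** The inconsistency is real and worth correcting, but it is modest. For non-dermatologic events, three of the four AE rows in Table 3 conflict with the literal text of 9.1.1. The consequence is conditional: a site that applied 9.1.1 as written would not send the sponsor a non-dermatologic SAE, SADE/USADE or ADE. The conclusion rests on reading the 9.1.1 sentence literally and on the absence of a stated order of precedence.

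Two stronger readings are not supported:

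- **That sites would in fact withhold such events.** Table 3, Section 11.2 and the monitoring provisions point the other way, and a site reading the whole protocol would probably report.
- **That the number of events at risk can be estimated from the earlier program.** Section 1.5 reports no related serious events in 627 subjects. That statement covers skin and non-skin events together, and some of the studies counted were still in progress, so it does not measure the non-dermatologic events at issue.

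No endpoint, analysis or sample size is affected.

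**What to change.** Reconcile the two sections by confining the 9.1.1 sentence to the residual class in Table 3. One way is to keep the existing words and qualify them: *Among AEs that are not SAEs, ADEs or SADEs/USADEs,* "only dermatologic AEs will be reported to the Sponsor"*; see Table 3.* At the same time, define *protocol specific* AEs in Section 9.0 consistently with Table 3 or delete the term, and make the same point in site training.

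This mirrors Table 3 and does not widen it. Non-serious, non-skin events attributed to the electrodesiccation or the anesthetic, and not to the CellFX System, would still fall in the dermatologic-only row, because the ADE definition refers to the investigational device. Extending reporting to procedure-related events is a separate choice for the sponsor and is not needed to remove the contradiction.

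The cost is one or two sentences in the protocol and a line in the training material. Compared with Table 3 as it stands, it adds no reporting duty.

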9.1.3 Serious Adverse Event (SAE) (ISO 14155:2011 3.37)

Adverse event that

- a) led to death,
- b) led to serious deterioration in the health of the subject, that either resulted in
 - 1) a life-threatening illness or injury, or
 - 2) a permanent impairment of a body structure or a body function, or
 - 3) in-patient or prolonged hospitalization, or
 - 4) medical or surgical intervention to prevent life-threatening illness or injury or permanent impairment to a body structure or a body function,
- c) led to fetal distress, fetal death or a congenital abnormality or birth defect.

NOTE 1: Planned hospitalization for a pre-existing condition, or a procedure required by the CIP, without serious deterioration in health, is not considered a serious adverse event.

9.1.4 Serious Adverse Device Effect (SADE): (ISO 14155:2011 3.36)

Adverse device effect that has resulted in any of the consequences characteristic of a Serious Adverse Event

9.1.5 Unanticipated Adverse Device Effect (UADE): (21CFR812.3)

Any serious adverse effect on health or safety or any life-threatening problem or death caused by, or associated with, a device, if that effect, problem, or death was not previously identified in nature, severity, or degree of incidence in the investigational plan or application, or any other unanticipated serious problem associated with a device that relates to the rights, safety, or welfare of subjects.

9.2 Device Deficiencies (ISO 14155:2011 3.15)

9.2.1 Definitions

Device Deficiency is an Inadequacy of a medical device with respect to its identity, quality, durability, reliability, safety, or performance.

NOTE: Device deficiencies include malfunctions, use errors, and inadequate labelling.

Device Malfunction is a failure of the study device to perform in accordance with its intended purpose when used in accordance with the instructions for use or study protocol.

9.3 Safety Reporting Requirements

Table 3 summarizes the time sensitive requirements for adverse events and device deficiencies. The Sponsor is the contact person for these reporting requirements.

Table 3. Investigator Responsibilities for Submitting Adverse Events to the Sponsor

Type of Adverse Event	Reporting Timeframe
*Serious Adverse Device Effects (SADE), including Unanticipated Serious Adverse Device Effect (USADE)	As soon as possible, but in no case later than 3 calendar days after the clinical site first learns of the event or of new information in relation with an already reported event
**Serious Adverse Events (SAE)	As soon as possible, but in no case later than 3 calendar days after the clinical site first learns of the event or of new information in relation with an already reported event
Adverse Device Effects (ADE)	As soon as possible, but in no case later than 3 calendar days after the clinical site study team first learns of the event or of new information in relation with an already reported event
All other AEs (dermatologic only)	Submit in a timely manner after the clinical site first learns of the event
**Device Deficiency with SADE potential	As soon as possible, but in no case later than 3 calendar days after the clinical site study team first learns of the deficiency or of new information in relation with an already reported deficiency
All other Device Deficiencies	Submit in a timely manner after the clinical site first learns of the deficiency

*The Sponsor will report the results of an evaluation of an unanticipated serious or serious adverse device effect to the FDA and all reviewing IRBs and investigators within 10 working days after the Sponsor first received notice of the adverse effect per 21 CFR 812.150.

**It is the responsibility of the investigator to inform their IRB of serious adverse events and device deficiencies as required by their IRB guidelines.

